#### **Procedures for monitoring enrollment and tracking/retaining participants for follow-up assessments:**

We have developed a procedure to ensure timely subject enrollment and data collection. Because of multiple samples (school staff & families), our monitoring and data collection procedure will occur in blocks based on sources of sample and carried out using a multiple-team-approach (a teacher/school staff data collection team, a parent-interview team, a child-assessment team, and a teacher EBI practice observation team). Designated research coordinators will be responsible for coordinating, tracking and collecting data from the school staff (head teachers, teachers, PTA) and families.

Research teams and coordinators will be trained to use a secure data tracking system to track and monitor the data tracking system on a weekly basis during enrollment or data collection periods. The monitoring will be conducted at the school level. For schools that do not meet the expected enrollment or assessment numbers will be flagged for additional actions. Research coordinators will follow up on those flagged schools to ensure they complete assessment according to the study timeline. The research coordinators will meet weekly with PIs to discuss the progress and share experience. We have applied this tracking approach in our previous studies.

#### **Strategies for Ensuring a diverse, representative sample:**

For teacher sample, all primary school teachers are eligible to participate. No one will be excluded. For families, they will be randomly selected from student lists provided by schools/teachers. Only 10% families will be selected for the evaluation study. Therefore, it is expected that our teacher and family recruitment samples will be representative.

#### **Potential recruitment/enrollment challenges and strategies for overcoming shortfalls:**

For school personnel recruitment, we anticipate that most teachers (>90%) will sign up for the study based on our prior experience. However, we anticipate some teachers will be on maternity leave, sick leave, or transferred to different schools during the study period. For those teachers, we will work with principals to determine alternative approaches to contact these teachers to gather data. A phone interview may be applied if such contact option is appropriate.

For families, we anticipate parents with low-literacy or struggling with poverty related stressors might be difficult to reach. If the situation happens, we will reach out to teachers and PTA for assistance in family recruitment and engagement. We will also apply strategies that we have learned from our previous studies, including sending home a reminder note to parent with students; calling parents; carrying out parent interview through home visits or phone calls.

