
*ParentCorps* model when implemented at scale and in diverse settings. The proposed *PD* study in Uganda will leverage this work and benefit from and contribute to scale-up of partnerships and effectiveness-implementation knowledge both domestically and internationally.

**Table 1. ParentCorps implementation models and impact evidence**

[figure not shown]
	United States (US)	LMICs- Uganda (urban) & Nepal (rural)
School-based Intervention Components	PD (3 days + 1:1 individual coaching) + Family Program (14 sessions).	PD (3-4 days+ a group coaching model to reduce costs and to align with value for working in groups as the “collective culture” + culturally relevant handout to facilitate discussion around EBI-strategies during parent-teacher meetings)
ParentCorps Contents	
 
Core EBI strategies included in PD & Family Program: Draw on social learning theory and cognitive & behavioral principles that target adults' knowledge, skills, and confidence in an effort to reduce or prevent child social, behavioral, and emotional problems). EBI strategies include: i) proactive behavioral management strategies; ii) social emotional promotion & regulation strategies; iii) managing misbehaviors & noncooperation; iv) school-family connection
 
Other EBI strategies included in PD: i) parent engagement strategies to strengthen school-home connection & support for students; ii) individual planning for supporting high-need students; and iii) coaching support in applying the EBI strategies.
 
	
Implementation model	Mental health professionals (MHPs) from an academic institution and Department of Education (DOE) jointly implemented PD and Family program	Localized Partnership Implementation Models Uganda (Urban): MHPs and psychiatric nurses implemented PD Nepal (Rural): MHPs, community health workers (CHWs), and District Education Office staff implemented PD
Targets in the studies	Ethnically diverse Black, Latino & Asian children (aged 4- 6) from low-income urban communities	Ethnically diverse children (aged 3-10) from low-income families in urban Uganda and rural Nepal with diverse tribes and migration backgrounds

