• **Teachers and PTA Members:** For the selected 36 schools, all pre-primary and Primary 1 to 4 teachers, serving students between 3 and 10 years old will be eligible to participate. Teachers' participation will be completely voluntary, with no consequence for opting out of participation due to personal reasons (see human subjects section for detail about teacher protection). PTA members from 24 intervention schools will be recruited to participate. For schools that do not have a PTA, Parent Leaders will be recruited. PTA members and Parent Leaders that are actively involved and have at least a year of experience in working with schools will be eligible. We will work with the intervention school to plan for recruitment and training of one PTA member from each intervention school (control schools will not have an identified PTA members). We anticipate that 540 teachers from 36 schools will participate in the evaluation study; and 360 intervention school teachers will be participated in intervention.

• **Families (Parent & child pairs):** Ugandan primary schools have on average about 550 students. Given the large numbers of students in schools, research staff will randomly select 10% of students and families from each school based on student lists provided by teachers (using random number generator software). Teachers will be informed of the students randomly selected for participation in the assessments and asked to introduce the study to the selected parents or primary caregivers. Targeted parents will be invited to consent for interviews, for teachers to complete ratings on their child's behavior, and for research staff to carry out objective assessments with their child.

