**To consent parents**, written or oral consent will be applied using local language (Luganda) or English, depending on parents' preference. Parents will be informed about the limitation to confidentiality, especially in adhering to legal status regarding reporting to child protection agencies if study children are found to be at-risk for abuse or neglect or are being abused or neglected. For parents who are literate, a written consent will be given, which will provide the names and contact information of the NYU and Ugandan investigators and Institutional Review Boards, a description of the study, including completing interviews (by research staff), allowing their child's teachers to provide data on their child behaviors at schools, allowing research staff to test their children, a description of potential risks and benefits, a statement of confidentiality, and an indication of the right to refuse or withdraw at any time without any consequence. The study staff will review this form in detail with parents to ensure informed consent. Parents who agree to participate in the study will sign the informed consent form. These data will be used for evaluation of PD effectiveness and quality of implementation. For parents who are illiterate or unaccustomed to dealing with forms, an oral consent will be given. Although oral consent does not require providing information on paper, the research staff are required to provide all the necessary information (describe above) to parents before obtaining their consent. For our study, we will provide an Oral Consent Card that provides the consent information in a bulleted list to parents. Information about the names and contact information of the NYU and Ugandan investigators and Institutional Review Boards Research staff will also be provided. Research staff will document the oral consent using digital recorder and in the research staff's notes. All parents of nursery to 4th grade students in intervention schools will be informed about PD program in their child's school. As part of the universal early childhood program provided by schools, families do not need to be consented. Only those participated in research activities will be consented.

Child assents to research will be obtained from the children above age 7 of parents who consent to the study

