### **13.3 Participant Reimbursements or Payments**

Because the training will be provided during non-school days and outside of the school, each teacher will receive US \$50 to compensate for travel and time. For PTAs' participation in training and engaging families, a small stipend of US \$30/month will be provided for the month they provide support. To increase control school motivation to participate and assist with data collection, a donation of US \$400 will be provided to each school at the end of the 1st year of participation in the study. In the later 2nd year of participation (after completion of the effectiveness evaluation), control schools will receive a one-day T-Wellness workshop (without PD) and 3 monthly follow-up group-support session.

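### Help with recruiting hard-to-reach families is not set up equally across arms, so who enters or stays in the child sample may differ by arm

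*Combined protocol and SAP*

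**What the plan says.** Section 4.4 (Families) draws a random 10% of pupils in every school. Teachers are told who was drawn "and asked to introduce the study to the selected parents or primary caregivers".

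The paragraph on enrolment shortfalls in the same section expects some difficulty: "we anticipate parents with low-literacy or struggling with poverty related stressors might be difficult to reach". If this happens, "we will reach out to teachers and PTA for assistance in family recruitment and engagement". It also lists "sending home a reminder note to parent with students; calling parents; carrying out parent interview through home visits or phone calls". None of these routes is limited to an arm.

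The PTA provision does differ by arm. Section 4.4 (Teachers and PTA Members) recruits one PTA member per intervention school and adds that "control schools will not have an identified PTA members". Section 5 has the PTA leaders attend the PD or PDT training, before the first school term. Section 13.3 gives, for their "participation in training and engaging families, a small stipend" of US $30 per month of support. In Section 1.1, the table of ParentCorps contents lists among the PD topics "parent engagement strategies to strengthen school-home connection". Section 11.3 adds that parents of nursery to fourth-grade "students in intervention schools will be informed about PD program".

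On timing, the Protocol Summary and Section 6.1 define T1 as before the intervention. Section 6.1 masks the staff who collect family and observation data.

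**The concern.** In a trial randomised by school, a random draw of pupils protects the comparison only if consent and retention do not depend on the school's arm. Here one fallback route for low-literacy and poverty-stressed families has a named, trained and paid person in two arms and no named counterpart in the third. In those two arms, the teachers who introduce the study are also trained in engaging parents.

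If condition is known when families are approached, or when they are traced at T2 and T3, the mix of families could differ between intervention and control before any effect on children. Masked data collectors protect measurement. They do not control who is approached, who agrees or who stays. Section 4.4 also rests its claim of a representative family sample on the random draw alone. Adjustment for the T1 score (Section 9) would remove only part of such a difference.

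**Working it through.** **1. The plan's counts.** 36 schools × 55 families = 1,980 pairs, as stated, and 12 × 55 = 660 per arm. One PTA leader in each of 24 intervention schools gives 24: 12 in PD, 12 in PDT, 0 in control. Section 4.4 puts average enrolment at about 550 pupils, and 10% of 550 is 55. The target therefore equals the full draw, so the routes for recovering hard-to-reach families matter.

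**2. Contact routes side by side.**

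| Route to families | PD and PDT schools | Control schools |
|---|---|---|
| Random 10% draw by research staff | yes | yes |
| Teacher introduces the study | yes; teachers are PD-trained at some point | yes; teachers not PD-trained |
| Notes, calls, home visits | yes | yes |
| PTA leader identified, trained and paid by the study | yes (24) | no (0) |

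The asymmetry lies between each intervention arm and control. PD and PDT have the same PTA provision.

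**3. Order of events.** T1 is defined as before PD. The workshop is before the first term (Section 5). The study timeline in Section 6.1 appears to place Cohort 1 family T1 in Term 1 of Year 2, which would be after the workshop. That table may be distorted in the text available, so this is only an indication. Being before the intervention is also not the same as being before condition is known, and no section fixes the second order. At T2 and T3, teachers and PTA leaders in intervention schools have been trained in any case.

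**4. Possible size.** The documents give no enrolment rate, no hard-to-reach share and no outcome gap, so every input below is an assumption:

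- *h*, hard-to-reach share of selected families: 10–40% (Section 1.1 puts chronic poverty at 38–43%, a loose upper guide)
- *p*, their enrolment without PTA help: 50–70%
- enrolment of other families: 90% in all arms
- *d*, gain from PTA help in intervention schools: 0–30 percentage points
- *g*, outcome gap between hard-to-reach and other children: 0.3–0.5 SD

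Share of hard-to-reach families among those enrolled:

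- control: s₀ = h·p / [h·p + (1−h)·0.9]
- intervention: s₁ = h·(p+d) / [h·(p+d) + (1−h)·0.9]
- bias before T1 adjustment = (s₁ − s₀)·g

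Results:

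- d = 0: bias 0.
- h = 0.2, p = 0.5, d = 0.2: s₀ = 0.10/0.82 = 12.2%, s₁ = 0.14/0.86 = 16.3%. The difference of 4.1 points gives 0.012 SD (g = 0.3) to 0.020 SD (g = 0.5).
- Extreme, h = 0.4, p = 0.5, d = 0.3: s₀ = 0.20/0.74 = 27.0%, s₁ = 0.32/0.86 = 37.2%. The difference of 10.2 points gives 0.031 to 0.051 SD. The upper value is 0.051/0.2 = 25.5% of the 0.2 SD benchmark in Section 9.

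With an assumed T1-to-outcome slope *b* of 0.5–0.6, T1 adjustment leaves (1−b) × 0.051, which is 0.020–0.026 SD in the extreme case.

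**The case against.** Much of the procedure is the same in all arms: the draw, the teacher introduction, and the notes, calls and home visits. Research staff take parental consent (Section 11.3). PTA help is conditional on difficulty arising. Section 4.4 says PTA without restricting it to the trained leaders, and nothing says that control schools lack an ordinary PTA. Each control school receives US $400, partly to encourage help with data collection. T1 is defined as before PD.

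These points defeat two stronger readings. A reader might infer that the composition of the child sample does depend on arm, because trained people who know the allocation recruit families only in intervention schools. The documents do not support this. If T1 precedes the workshop as defined, nobody is trained at enrolment; and if condition is known by then, control teachers know theirs too. A reader might also assume a large gap in overall enrolment, say 85% against 70%. With non-enrolled children 0.5 SD worse, that gives 0.5 × 0.15 = 0.075 SD. But PTA help reaches only a subset. With 40% hard to reach and the rest enrolling at 90%, that gap needs hard-to-reach enrolment to rise from (0.70 − 0.54)/0.40 = 40% to (0.85 − 0.54)/0.40 = 77.5% through this route alone.

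The asymmetry itself still stands. An ordinary PTA in a control school is not identified, trained or paid by the study, and Section 4.4 supplies a Parent Leader where there is no PTA only for intervention schools. The US $400 goes to the school at the end of its first year, not to a family contact. The order of consent and disclosure remains unstated, and the retention route remains open even if T1 comes first.

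**Conclusion.** The point holds as a risk. The planned help for reaching difficult families differs by arm, and no section places family consent and T1 before condition is disclosed. Who enters, or is retained in, the child sample may therefore differ between each intervention arm and control. The documents do not show that it does.

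The likely size is modest: 0 to about 0.05 SD before T1 adjustment, and about half of that or less afterwards, resting wholly on the assumed inputs above. If the added families have children with worse outcomes, the bias works against PD and PDT and could hide part of a real effect. If they do not, the sign could change. The change deserves making because it is cheap before enrolment and selection cannot be fully repaired by analysis afterwards.

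**What to change.** 1. In Section 4.4 (enrolment challenges), specify the same family-contact help in all 36 schools at T1, T2 and T3. One option is not to use the study's PTA leaders for research recruitment or tracing, and to rely on the notes, calls and home visits already listed. The other is to have every school, control included, name an equivalent contact who is not trained in PD.
2. In Sections 4.4 (Families) and 6.1, state that in each cohort the random draw, family consent and T1 interview are completed before schools learn their condition and before the workshop. Reconcile Section 5 and the study timeline with that order.
3. Report families selected, approached, enrolled and retained by arm.

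The sample size and intervention content are unchanged. Without PTA leaders, recruitment of hard-to-reach families may be somewhat slower, and some low-literacy families could be missed; the common-contact option limits that loss. The order in item 2 tightens the schedule before the workshop, because about 990 families per cohort must be enrolled and interviewed first.

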### ***Evidence to support the feasibility of enrollment***

Our research team has track record in conducting large scale studies both in the US and in Ugandan contexts. We have developed family and school engagement strategies to ensure high rate of enrollment. We have also applied a multiple-team approach (by having multiple research coordinators) and a partnership approach (partnering with research network, academic social science/public health departments, and community networks to utilize additional network strategies) to ensure target enrollment and timely data collection. Given our prior experience, we have demonstrated the feasibility of our enrollment approach

#### ***4.5 Duration of Study Participation***

During Year 1, we will establish a localized scalable PD implementation team structure and train a group of PD/PDT implementers (N=8; using a TTC-MOE-Mental Health partnership structure). We will train an implementation team that includes 6 TTC trainers and 2 MHPs (i.e., clinical psychologists, senior psychiatric nurses) and additional educational stakeholders (i.e., governmental stakeholders from MOE, MOH) from the 2 regions. As with the methods that we have applied before, we will refine and formalize the partnership by using a multi-stakeholder participatory approach and principles of effective partnership. Our partnership process, meetings, field interview notes, and qualitative data will be documented and analyzed. The implementation team members will participate in the study for 4 years.

T-Wellness Package User-Centered & Optimization Study (N=60). T-Wellness Package will be based on the *Stress and Coping* (SC), a group-approach EBI that has been shown to reduce stress for Ugandan adults impaired by distress in PI-[name]'s prior RCT work (effect size  $d=.35$ ). The SC focuses on understanding personal stress/adversity, and strategies for managing problems/stress, mood, strengthening social support, and staying well. To effectively address teacher burnout, we will add additional strategies from the Rational-Emotive Health Education Intervention (REHET), which focuses on evidence-based strategies to improve cognitive-behavioral skills and techniques to help teachers manage workplace burnout stress and overcome irrational beliefs in teaching. These strategies have shown to be effective in reducing teacher burnout related stress in LMICs. Our T-Wellness package will optimize these two core components of the evidence-based stress and support interventions that are relevant to teacher stress and have been reported in the literature (see Box 1 for T-Wellness contents). To ensure the expected impacts for T-Wellness, we will recruit 4 study schools and applying factorial design to test the effect of each component (1 Common Stress management; 1 Burnout Stress management; 1 Combined Common and Burnout Stress management; 1 control; with ~15 teachers in each condition). Teacher participants will participate in the study for 4-6 months. We will collect pre- and post-intervention data using a mixed-methods design to evaluate the effect of each component on stress management indicators (e.g., stress management skills, competency, burnout, general personal stress). Results will be used to optimize stress intervention components to be included in the Year 2-4 RCT). PI [name] and consultant [name] with stress management expertise will lead this effort.

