Description of Study Intervention/Procedure	

• Prior to the RCT study (or during Year 1), T-Wellness Package (a brief teacher stress management psychoeducation package, adapted from EBIs and including a half-day workshop for common stress management and a half-day for burnout management, and three follow-up group support sessions) will be tested to insure user-centeredness. we will recruit 4 study schools and applying factorial design to test the effect of each component (1 Common Stress management; 1 Burnout Stress management; 1 Combined Common and Burnout Stress management; 1 control; with ~15 teachers in each condition). Both groups' will also receive 3 post-workshop group support sessions. We will compare pre-post differences on teacher stress management and mental health using a mixed-methods data collection.

• To implement PD/PDT using a scalable approach, we will formalize partnership with the Ugandan Ministry of Education (MOE), Ministry of Health (MOH), academic medical center, and Teacher Training Colleges (TTCs) stakeholders in Year 1. The partnership and intervention implementation team will receive training from NYU PD trainers, and implement PD/PDT in Years 2-4.

• To study effectiveness-implementation aims (Aim 1-3), a cRCT will be conducted. Public primary schools from Kampala/urban and Hoima/ rural will be recruited. A stratified-block randomization procedure will be applied to ensure approximately similar characteristics across geographic regions and three intervention conditions (PD, PDT, and control). Teachers from the PD will receive a 3-day training, and teachers from the PDT will receive a 4-day training. Both intervention groups will receive 8 group-coaching sessions (with teachers from their own school). Teachers from the control schools will receive child mental health promotion materials. They will receive T-Wellness in Year 4 after the evaluation study is completed. Given the large numbers of students in schools, research staff will randomly select 10% of students and families from each school for participation in the evaluation study. A total of 1,980 families (parent-child pairs) from 36 schools (averaging 55 families/per school) will participate in the evaluation study. Effectiveness outcomes will be assessed at 3 time points over 18 months (baseline/T1, post-PD or PDT, 5-6 month/T2, and 16-18-month follow-up/T3). Objective observation, implementers, school staff, parent, and child report data (quantitative and qualitative) will be gathered.

• To study underlying mechanisms, we will use the evaluation data describe above to examine whether intervention effects on children's mental health outcomes is mediated through improvement on teachers' EBI practices (primary) and teacher stress coping. To study moderation mechanisms, geographic region, fidelity (including adherence, quality of program implementation, engagement, exposure) and other implementation contextual factors (i.e., EBI fidelity, school climate), guided by the Consolidated Framework for Implementation Research, will be studied.

• Identifiers will be removed from the identifiable survey and field notes. Data may be used for future research studies or shared with other researchers and we will not request additional informed consent from you to use these specimens as we have noted here.

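### The Year 1 T-Wellness study has one school per condition, so it can describe change by school but cannot test component effects or guarantee impact

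*Combined protocol and SAP*

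**What the plan says.** The design appears in the Protocol Summary (Description of Study Intervention/Procedure) and in section 4.5. Four schools are recruited, with one school for each of common stress management, burnout stress management, the two combined, and control: "1 control; with ~15 teachers in each condition". The Population entry of the Protocol Summary adds that the 60 teachers come from four schools outside the cRCT.

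Two kinds of purpose are given.

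- **User-centred.** In the Protocol Summary the package "will be tested to insure user-centeredness", and section 3.1 also calls this a user-centred testing study.
- **Effect-testing.** The Protocol Summary speaks of "applying factorial design to test the effect of each component". Section 4.5 says "we will recruit 4 study schools and applying factorial design to test the effect of each component" and adds that pre-post data are collected "to evaluate the effect of each component on stress management indicators". It opens the aim with "To ensure the expected impacts for T-Wellness". The Innovation text under section 1.2 likewise says that the approach ensures T-Wellness impact before the cRCT starts.

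On analysis, the only statement is "We will compare pre-post differences on teacher stress management and mental health using a mixed-methods data collection". On use, section 4.5 says "Results will be used to optimize stress intervention components to be included in the Year 2-4 RCT". Section 9 covers Aims 1-3 and the qualitative data, and gives no model, error rate or decision rule for the Year 1 comparison.

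**The concern.** With a single school in each condition, the school is the condition. A new head teacher, a heavier workload or a local event during the study period would move all the teachers in that school together, and would look exactly like an effect of the component given there. A pre-post comparison removes stable differences between schools, but not differences in how schools change.

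The protocol applies this principle to the main trial: section 6.1 randomises schools, and section 9 includes school random intercepts. Nothing comparable is stated for Year 1.

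What is at stake is the content of T-Wellness and what is later claimed for it. A school-specific or chance change could be read as a component working or failing. It could then shape what enters the cRCT, or be cited as quantitative evidence on a single component.

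**Working it through.** **1. The plan's own figure.** 4 schools x about 15 teachers = 60, which agrees with the N=60 in section 4.5. No power, alpha or detectable effect is stated for this study, so there is nothing further to reproduce.

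**2. Degrees of freedom.** There are four school means.

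- Full 2x2 (intercept, two main effects, interaction): 4 - 4 = 0 df for between-school error.
- Additive model (no interaction): 4 - 3 = 1 df. The two-sided 5% critical t on 1 df is 12.71.

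This step needs no assumed ICC or effect size.

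**3. Inputs for an illustration.** The number of teachers per school, m = 15, is from the documents. The effect d = 0.35 is the figure section 4.5 reports for the source intervention in distressed Ugandan adults. Using it for one component, in units of the SD of the change score, is my assumption. The ICC of the change score, 0.01 to 0.20, is also assumed, as are a two-sided 5% test and no dropout.

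**4. Formulas.** With change-score variance 1, the variance of a school mean is v = ICC + (1 - ICC)/15. A main effect compares two schools with two, so its variance is v/2 + v/2 = v and its SE is sqrt(v). School-level power comes from the noncentral t with 1 df and noncentrality d/sqrt(v). The chance that the estimate has the wrong sign is Phi(-d/sqrt(v)).

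| ICC | v | SE | d/SE | Power, 1 df | Wrong sign |
|---|---|---|---|---|---|
| 0.01 | 0.0760 | 0.276 | 1.27 | 8.5% | 10% |
| 0.05 | 0.1133 | 0.337 | 1.04 | 7.5% | 15% |
| 0.10 | 0.1600 | 0.400 | 0.88 | 6.8% | 19% |
| 0.20 | 0.2533 | 0.503 | 0.70 | 6.2% | 24% |

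**5. No clustering at all.** With ICC 0, a main effect compares 30 teachers with 30. SE = sqrt(2/30) = 0.258, d/SE = 1.36, power about 27%, wrong sign 9%. One condition against control (15 versus 15) has SE = sqrt(2/15) = 0.365 and power of about 15-16%. For 80% power at d = 0.35, 129 teachers per group would be needed. At the low end of the ICC range, small numbers are therefore the main cause of the poor precision.

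**6. More teachers would not cure it.** As m grows, the SD of a pure school-versus-school difference falls only to sqrt(2 x ICC). That is 0.32 at ICC 0.05 and 0.45 at ICC 0.10, close to or above the 0.35 being sought.

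**7. Sensitivity to scale.** If d = 0.35 is in raw-score SD, it becomes 0.35/sqrt(2(1 - r)) in change-score SD, where r is the pre-post correlation: 0.296, 0.350 and 0.452 for r = 0.3, 0.5 and 0.7 (assumed). Over these and the same ICC range, power runs from 5.8% to 10.5% and wrong sign from 5% to 28%. The conclusion does not change.

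**The case against.** The strongest reply is that this is a small preparatory study in schools outside the trial. It has a user-centred, mixed-methods purpose and no formal test in section 9, and one of the two claims of ensured impact sits in the Innovation text, which governs no analysis. All of that is true, and it keeps the point minor. It does not remove it, because section 4.5 also sets an effect-testing aim and feeds the results into the components of the cRCT.

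The illustration also rests on assumptions: no ICC is given, and 0.35 belongs to a whole intervention in a different group. That stands too, which is why the argument rests on step 2.

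Four stronger readings are tempting but are not supported by the documents.

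- **The labels are wrong.** Control, A, B and A+B do form a 2x2, so factorial is accurate as a description of layout. The documents never define what MOST requires, so they give no basis for saying the study falls short of it.
- **The main trial is compromised.** The cRCT randomises other schools, and its comparisons are not biased by how T-Wellness was refined.
- **Year 1 cannot matter because the package is fixed.** Format and length are stated (Protocol Summary, Box 1, section 5). But the Study Duration entry has PDT content being finalised in Year 1, and section 4.5 still leaves components to be optimised.
- **Teachers will be analysed as independent, with an inflated type I error.** The plan names no such analysis.

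**Conclusion.** The concern holds as a minor one, and the text is wrong as written. The confounding of condition with school follows from the stated layout alone, and so do the 0 and 1 df. The figures of about 6-9% school-level power and 10-24% wrong sign depend on d = 0.35 in change-score SD and ICC 0.01-0.20; the roughly 27% power without clustering depends on the same d. No value in these ranges makes the study a usable test of a component. It can serve its user-centred purpose and describe change in each school. It cannot test or evaluate component effects, and it cannot ensure impact.

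**What to change.** Three edits are enough.

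1. **Aim (Protocol Summary and section 4.5).** Keep the four-condition factorial layout. Replace the wording about testing, and in section 4.5 also about evaluating, each component's effect with: *to assess user-centredness and describe pre-post change in the listed stress-management indicators by school, using mixed methods*.
2. **Use of results (section 4.5).** Restate the sentence on optimising components as: *User-centredness and qualitative findings, together with descriptive pre-post change, will be used to refine T-Wellness content. Any between-school difference is exploratory, is confounded with school, and will not by itself be grounds for adding or dropping a component.*
3. **Claims of ensured impact.** Delete "To ensure the expected impacts for T-Wellness" in section 4.5. In the Innovation text, change the statement that impact is ensured to: *allows T-Wellness content to be refined*.

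No edit to the words MOST or factorial is needed.

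The cost is wording only: the same four schools, about 60 teachers and data collection, and between-school estimates can still be reported. The downside is that Year 1 can no longer be cited as quantitative evidence on single components. To keep a testing aim instead, the study would need several schools per condition and a school-level analysis, which is a larger study.
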